6.1.3 Primary [REDACTED], with rationale for their selection and measurement

[figure not shown]
6.1.3.1 Primary performance endpoint

The primary performance endpoint is the change from baseline in total ocular surface staining. It is the most commonly used endpoints in clinical trials with DED patients. It is performed to detect ocular damage surface, which is considered as a hallmark sign of DED.

Thus, the change from baseline (Day 1) in total ocular surface staining grade according to Oxford 0-15 grading scheme (corneal and conjunctival staining by fluorescein with a yellow filter) at D36 in the study eye [REDACTED] was set as the primary performance endpoint to evaluate the performance of the treatment.

[REDACTED]

Different ocular surface staining scales have been developed and despite common usage, a universally accepted “gold standard” grading scale does not exist for corneal and conjunctival staining. This investigation will use the Oxford scale, a widely used and standardised grading scale. International regulatory agencies such as the Food and Drug Administration (FDA) rely on corneal and conjunctival staining measurement as a primary endpoint in clinical trials of commercially registered dry eye treatments (Begley et al. 2019).

6.1.3.3 *Safety endpoints*

The following safety and tolerability endpoints will be assessed:

- Ocular and systemic TEAE,
- Ocular and systemic Serious TEAE,
- Ocular and systemic TEAE leading to premature IMD discontinuation,
- Ocular and systemic IMD related TEAE

6.1.4 Methods and Timing for Assessing, Recording, and Analysing Variables

Four visits are scheduled during the course of the investigation as presented below:

Visit #1: Day 1-10/Day 1-7 Screening visit (run-in period)

Visit #2: Day 1 Randomisation visit (D1)

Visit#3: Day15 (± 1 day) (D15)

Visit #4: Final visit Day 36 (+3 days) or premature discontinuation visit.

Visits should be performed at the same hour (± 4 hours)

The schedule of visits, including the timing of examinations and assessments is presented in **Table 2 Schedule of Visits and Procedures**

Screening Period

Visit#1: Screening visit (Day1-10/Day1-7)

Visit#1 will consist of the following procedures and examinations to be done according to the following order and in each eye.

Visit#1 will consist of the following procedures by the masked investigator or authorised delegate who will perform the ophthalmologic examination during all the visits.

By the masked investigator or delegate for selected tasks (according to local requirements, the investigator may delegate tasks to collaborator)

- Information for the patient and signature of the consent (can be done up 7 days before this visit). See **Section 13.**
 - ✓ On paper CRF
 - Ocular discomfort (VAS)
- ✓ On eCRF
- Demography
- History of dry eye
- Urine pregnancy testing
- Questioning about ocular and systemic medical and surgical history (other than dry eye)
- Questioning about previous and concomitant ocular and non-ocular treatments
- Measurement of Far BCVA
- Questioning about ocular symptoms within the last 48 hours
- Slit lamp examination for measuring*:
 - Measurement of conjunctival hyperaemia with [REDACTED] photographic scale
 - TBUT

- Oxford 0-15 grading scheme (corneal and conjunctival staining by fluorescein with a yellow filter)
- Schirmer test without anaesthesia,
- Verification of inclusion and exclusion criteria,
- Status of the patient, (start of run-in period or not),
- Run-in treatment dispensation,
- Patient diary dispensation (instructions)**.

* Examination must be performed by the masked investigator or delegate for selected tasks for all visits and using the same slit lamp.

** The patient diary will be an aid to compliance assessment, it will not be recorded in the database.

The next visit must be scheduled between 7 and 10 days after Visit#1 at the same hour (\pm 4 hours).

Treatment Period

Visit#2: Randomisation visit (Day 1)

Visit#2 will consist of the following procedures and examinations to be done according to the following order and in each eye.

Visit#2 will consist of the following procedures and examinations by the masked investigator or authorised delegate who will perform the ophthalmologic examination during all the visits.

By the masked investigator (the same as the screening visit) **or delegate for selected tasks** (according to local requirements, the investigator may delegate tasks to collaborator)

- ✓ On paper CRF
- Questionnaire (OSDI)
- Ocular discomfort (VAS)

- ✓ On eCRF
- Questioning about ocular symptoms within the last 48 hours
- Questioning about Hydrabak® compliance during run-in period and last instillation (at least 6 hours) before the visit and check of the patient diary completion with the patient,
- Questioning about previous and concomitant ocular and non-ocular treatments
- Slit lamp examination for measuring*:
 - Measurement of conjunctival hyperaemia with [REDACTED] photographic scale
 - TBUT
 - Oxford 0-15 grading scheme (corneal and conjunctival staining by fluorescein, with a yellow filter),
- Schirmer test* (without anaesthesia),
- AE reporting
- Verification of inclusion and exclusion criteria
- Status of the patient
- Randomisation
- IMD dispensation

- Patient diary dispensation. The patient who will be instructed to instil the IMD in both eyes and report in the patient diary the number of instillations/day and to bring back it at each visit.

* Examination must be performed by the same **masked investigator or delegate for selected tasks** for all visits and using the same slit lamp.

The next visit must be scheduled in 15 days (± 1 day) at the same hour (± 4 hours).

Visit#3: Day 15 (± 1 day)

Visit#3 will consist of the following procedures and examinations to be done according to the following order and in each eye.

By the masked investigator (the same as the screening visit) **or delegate for selected tasks** according to local requirements, the investigator may delegate tasks to collaborator)

- ✓ On paper CRF
- Questionnaire (OSDI)
- Ocular discomfort (VAS)

- ✓ On eCRF
- Questioning about ocular symptoms upon instillation
- Questioning about ocular symptoms within the last 48 hours
- Questioning about soothing sensation 15 min after IMD instillation
- Assessment of global patient satisfaction with the use of bottle
- Assessment of global satisfaction by the patient
- Assessment of the ocular tolerance by the patient
- Questioning about ocular and non-ocular concomitant treatments
- Review of the completion patient diary
- Questioning about IMD dose regimen compliance
- Slit lamp examination for measuring*:
 - Measurement of conjunctival hyperaemia with [REDACTED] photographic scale
 - TBUT
 - Oxford 0-15 grading scheme (corneal and conjunctival staining by fluorescein with a yellow filter),
- Schirmer test* (without anaesthesia),
- AE reporting
- Device deficiency
- Assessment of the ocular tolerance by the investigator
- Assessment of the performance by the investigator

* Examination must be performed by the same **masked investigator or delegate for selected tasks** for all visits and using the same slit lamp.

By the unmasked collaborator:

- Recording the number of returned used and unused IMD in document source (the accountability is expected for the amount of bottles) and transfer this information to masked investigator.

The next visit must be scheduled at Day 36 later (+3days)

Visit#4: Day 36 (+3days)

Visit#4 will consist of the following procedures and examinations to be done according to the following order and in each eye.

By the masked investigator (the same as the screening visit) or delegate for selected tasks (according to local requirements, the investigator may delegate tasks to collaborator).

- ✓ On paper CRF
- Questionnaire (OSDI)
- Ocular discomfort (VAS)

- ✓ On eCRF
- Questioning about ocular symptoms upon instillation questionnaire
- Questioning about ocular symptoms within the last 48 hours
- Questioning about soothing sensation 15 min after IMD instillation
- Assessment of global patient satisfaction with the use of bottle
- Assessment of global satisfaction by the patient
- Assessment of the ocular tolerance by the patient
- Questioning about ocular and non-ocular concomitant treatments
- Measurement of Far Best Corrected Visual Acuity,
- Review of the completion patient diary
- Questioning about IMD dose regimen compliance
- Slit lamp examination for measuring*:
 - Measurement of conjunctival hyperaemia with [REDACTED] photographic scale
 - TBUT
 - Oxford 0-15 grading scheme (corneal and conjunctival staining by fluorescein, with a yellow filter),
- Schirmer test* (without anaesthesia),
- AE reporting
- Device deficiency
- Assessment of the ocular tolerance by the investigator
- Assessment of the performance by the investigator
- Status of the patient

* Examination must be performed by the same masked person for all visits and using the same slit lamp.

By the unmasked collaborator:

- Recording the number of returned used and unused IMD in source document (the accountability is expected for the amount of bottles), and transfer this information to masked investigator.

Premature discontinuation Visit during the investigation

A patient who prematurely discontinues from the investigation should have, if possible, a premature discontinuation visit. This last site visit should take place as soon as possible after the patient stops taking IMD. All follow-up procedures and examinations scheduled to be performed at the final visit should be performed at the patient's premature discontinuation visit.

If the patient is tested COVID-19 positive during the course of the study, the patient has to inform the investigator. Either the patient may continue the investigation when he/she can follow the protocol requirements safely and in accordance with the national/regional recommendations or the patient may be withdrawn from the investigation. The last site visit should take place as soon as possible after the patient stops taking IMD.

Note: Randomised patients who withdraw will not be replaced by another subject. The subject number and associated randomisation number of the withdrawn subject must not be reassigned to a different subject.

Adaptive Follow-Up of Patients Prematurely Withdrawn due to an Exceptional Circumstance (e.g. COVID-19 pandemic)

If the patient withdrew from the investigation due to an exceptional circumstance, and if an onsite visit was not authorised, a premature discontinuation visit by phone is required.

– **Premature discontinuation phone call**

- Check the IMD compliance with the patient
- Instruct the patient to stop the IMD and keep used and unused IMD for later return
- Ensure the continuity of artificial medication as per routine clinical practice
- Collect AE/Serious Adverse Event (SAE) and any changes in concomitant treatments
- Collect DD
- Plan a safety onsite visit 4 weeks later (± 7 days) and ensure that the patient understands all recommendations
- Record the phone call and all information collected in the patient medical record

Safety Follow-up visit on site¹

During the onsite follow-up visit done 4 weeks later (± 7 days) after the premature discontinuation phone call, the following procedures are required:

- Check the IMD compliance with the patient
- Record the number of the returned used and unused IMD (by the authorised unmasked delegate)
- Check that the patient had stopped the IMD and takes the new treatment, collect start and end dates of these medications
- Ensure that dry eye is well controlled
- Collect AE/SAE and any changes in treatments
- Record the visit and all information collected in the patient medical record

6.1.5 Equipment to be used for Assessing the Clinical Investigation Variables and Arrangements for Monitoring Maintenance and Calibration

A slit lamp will be used to measure the primary endpoint “Total ocular surface staining grade”. During the Site Qualification Visit and the Site Initiation Visit, the site must prove that he has a maintenance certificate for the slit lamp. During the study, the monitor should verify that the maintenance is performed (cf. manufacturer guidelines).

During the study, the same slit lamp must be used for the same patient at each protocol visit.

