6.2 IMD(S) AND COMPARATOR(S)

6.2.1 Description of the Exposure to the IMD

IMD will be administered by the patient every day for 36 + 3 days, one drop in each eye 3 to 6 times daily into the lower conjunctival sac of each eye.

No IMD instillation at least 2 hours before Visit#3 and 4. However, the first instillation can be done any time after the patient has completed the randomisation visit.

There will be two treatment groups:

- T2769 (test device)
- Vismed® Multi (reference device)

A detailed description of T2769 and of Vismed® Multi is available in **Section 2**.

6.2.2 List of any Other Medical Device or Medication to be Used during the Clinical Investigation

Run-in Treatment/Wash-out Treatment

Once all screening criteria have been checked, the patient will receive a box containing 1 bottle of Hydrabak® treatment for the run-in period between Day-10/-7 to Day 1. 1 drop in each eye 3 to 6 times daily

Hydrabak® is an unpreserved NaCl 0.9% ophthalmic solution supplied in a 10 ml multidose ABAK® system bottle. Hydrabak® will be provided by Laboratoires Théa.

Table 6 Run-in Medical Device Sodium Chloride (Hydrabak®)

Ingredient	Function	Percentage formula (g/100 mL)
Sodium Chloride	Isotonising agent	0.900
Disodium phosphate rate	pH Buffer	0.317%
Sodium dihydrogen phosphate	pH Buffer	0.067%
Water for injections	Vehicle	Ad 100 mL

Batch number and expiration dates will be specified on the packaging.

Auxiliary Products

An auxiliary product is defined as a product used on site for the needs of a clinical investigation as described in the CIP, but not as an IMD.

Fluorescein Faure 0.5% unidoses: one drop will be instilled in the upper bulbar conjunctiva of each eye by the investigator at each visit to perform the slit lamp examination: TBUT and Corneal staining with Oxford 0-15 grading scheme. This staining is assessed with a yellow filter.

Schirmer-Plus: While the patient looks upwards, the lower lid will be drawn gently downwards and temporally. The rounded bent end of a sterile Schirmer test strip will be hooked in the lower conjunctival sac over the temporal one-third of the lower eyelid margin. After five minutes, the moistened paper is removed and the length of the tear absorption on the strip will be measured (in millimeters).

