6.4.1.3. Safety measures

Adverse Events and device deficiencies Ocular and systemic AEs will be collected by the investigator (or authorised assessor/delegate) at each visit.

In case of appearance of a new clinically significant sign or symptom, it should be reported as an AE or SAE.

In case of clinically significant worsening of a pre-existing sign or symptom, it should be reported as an AE or SAE.

The handling of AEs is detailed in **Section 14**.

DD will be also collected.

- Ocular Symptoms Upon Instillation,

The severity of ocular symptoms upon instillation will be assessed by the patient.

“Since the last visit, have you felt any unusual ocular sensation immediately after study treatment instillation (s)?

The following symptoms will be evaluated:

- Burning/Irritation
- Stinging/Eye Pain
- Itching/pruritus
- Eye dryness feeling
- Foreign body sensation
-

Severity will be assessed based on a 4-point scale:

- 0 = Absent,
- 1 = Present but not disturbing,
- 2 = Disturbing
- 3 = Very disturbing.

The translation of these terms will be provided to the site.

- Visual Acuity

Far (BCVA) will be assessed in each eye using the same chart throughout the study. It can be expressed using units as /10, decimal notation, MAR, logMAR, EDTRS or Snellen notation. It will be analysed after conversion in LogMar. [REDACTED]).

- Ocular Tolerance Assessment by the investigator

The investigator has to answer to the following question in local language:

“How do you consider the IMD ocular tolerance?

- Very satisfactory
- Satisfactory
- Not very satisfactory
- Unsatisfactory”

- Ocular Tolerance Assessment by the Patient

The investigator has to ask the patient the following question in local language:

“How do you consider the study treatment ocular tolerance?

- Very satisfactory
- Satisfactory
- Not very satisfactory
- Unsatisfactory”

- Treatment Compliance Evaluation

Patient will return all investigational products (IMDs and Hydrabak®), whether used or unused.

For Hydrabak and IMD (T2769 or Vismed® Multi), the patient will also have to report information about his/her compliance on a paper patient diary during the treatment period. Each day the patient will enter the date and number of instillations* per day. Moreover, it will be asked to add the date and hour of last instillation before the beginning of each study visit.

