6.4.7 Recommended Follow-Up Address after the Clinical Investigation

Not Applicable

6.5.1 **Source Documents**

Each participating investigational site will maintain appropriate medical and research records in compliance with ISO14155 and any other regulatory and institutional requirements for the protection of patient's confidentiality.

Source data are all information in original records and certified copies of original records of clinical findings, observations, or other activities in a clinical investigation necessary for the reconstruction and evaluation of the investigation. Source data are contained in source documents.

Source documents are any original documents, data and records. These may include, but are not limited to, patient medical records, hospital charts if any, clinic charts, laboratory notes, patient's questionnaires, patient's diaries if any, the investigator's files, pharmacy dispensing records and recorded data from automated instruments.

Some specific medical data gathered during routine medical practice visits prior to the participation can be used in screening visit and before informed consent form on the patient best care interest.

All following patient's assessments will be collected via a paper diary and paper questionnaire and will be considered as source data:

- Run-in treatment compliance: number of instillations/day
- IMD compliance: number of instillations/day
- OSDI questionnaire
- VAS

The following information should be entered into the patient's medical record:

- Patient's name, date of birth, gender
- Patient's contact information
- The date the patient entered the study and patient's number
- The study title and/or the clinical investigation number
- A statement that informed consent was obtained (including the date) and patient's card was provided to the patient; data protection consent or other country and local patient privacy required documentation for this investigation have been obtained (including the date)
- Date of all patient's visits
- Investigated disease history:
 - o Diagnosis of DES for each eye

- Date of onset of the diagnosis in each eye (months/year)
- Previous use of artificial tears
- Ocular and systemic medical and surgery history (other than dry eye)

For systemic medical history, the information could be collected via patient interview. For ophthalmic medical history of referred patient's, a letter from the referring ophthalmologist is strongly recommended.

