6.5.2 Source Data Verification

One of the primary responsibilities of monitoring is the review of source documentation (SDR= Source Data Review) to check quality of source, review CIP compliance, ensure the critical processes and source documentation are adequate, to ascertain Investigator involvement and appropriate delegation and assess compliance to other areas (e.g; SOPs, GCP, ISO 14155 current version). This will require direct access to all source documents, any original documents, data and records of each patient.

It will be verified that informed consent documentation is filed for all screened patients whether or not they were randomised into the investigation and that the information is listed in the source documents.

Source Data Verification (SDV) will be recorded in e-CRF and SAE/pregnancy related documents, consisting in a comparison of the source documentation and other records relevant to the investigation.

The SDV will ensure the data are Attributable, Legible, Contemporaneous, Original, Accurate, complete, consistent, enduring and available (ALCOACCEA guiding principles).

Source Data Monitoring combines:

- ✓ Site Monitor review of the source data for a subject in order to confirm that the site is compliant with ICH GCP and the Protocol
- ✓ Evaluation of the conformity of the data presented in CRF, or other Sponsor-provided documents, with the available Source Data

SDR can be done alone, but SDV cannot be done without prior SDR, since validating data transcription is not useful if protocol and GCP compliance have not been confirmed first.

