7.1 ANALYSIS POPULATION AND PROCEDURES

The following analysis sets will be considered:

- **Safety set:**

All enrolled patients, having received at least one dose of IMD and analysed as treated.

The safety set will be the primary population for safety analysis.

- **Intent-to-treat (ITT) set:**

All randomised patients and analysed as randomised.

- **Full analysis set (FAS):**

All randomised patients, having received at least one dose of IMD, with at least one baseline and one post-randomisation performance assessment on treatment and analysed as randomised.

The FAS will be the primary population for performance analysis.

- **Per protocol (PP) set:**

[figure not shown]
Subset of the FAS including patients without any major CIP violations likely to seriously affect the primary outcome of the study. Deviations from the CIP will be defined and assessed as “minor” or “major” in cooperation with the Sponsor during a blind review meeting before the database lock.

The PP set will be considered as secondary population and will be used for sensitivity analyses of the primary [REDACTED] endpoints. Patients will be analysed as treated.

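### Is the 2-hour no-instillation rule left unchecked before the D36 Oxford reading?

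*Protocol*

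**What the plan says.** Protocol 6.2.1 sets the rule: "No IMD instillation at least 2 hours before Visit#3 and 4". The Oxford score is read at both visits, and both readings enter the primary repeated-measures model (Protocol 7.2.1, SAP 3.4.1).

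Protocol 6.1.4 lists the procedures for each visit.

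- **Visit 2**, under the eCRF heading: "Questioning about Hydrabak® compliance during run-in period and last instillation (at least 6 hours) before the visit".
- **Visits 3 and 4**, under the same heading: a review of the patient diary, then "Questioning about IMD dose regimen compliance", then the slit lamp examination. The last instillation is not named.
- **Visit 1**, a footnote to the dispensing of the run-in diary: "The patient diary will be an aid to compliance assessment, it will not be recorded in the database".

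Protocol 6.4.1.3, under treatment compliance, says of the paper diary that "it will be asked to add the date and hour of last instillation before the beginning of each study visit". It also has compliance checked by questioning the patient and by looking at the diary.

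Protocol 6.5.1 counts patient diaries among the source documents. Its list of patient-completed source data gives "IMD compliance: number of instillations/day" and does not mention the hour. Under 6.5.2, monitors review source to "review CIP compliance, ensure the critical processes and source documentation are adequate".

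The per-protocol set is defined as "Subset of the FAS including patients without any major CIP violations likely to seriously affect the primary outcome of the study". Deviations are classified at a blind review before database lock (Protocol 7.1 and 10, SAP 3.2.5). SAP 3.3.8 says that IMD administration and compliance data will be listed.

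**The concern.** The sponsor evidently wants a recent drop kept out of the reading. The baseline visit has a named question for this, and the visit that supplies the primary endpoint appears to have none. If the hour exists only on paper and the paper never reaches the database, a statistician could not derive breaches from the data. The per-protocol analysis could then miss them, and the report could not show that the two arms were read under the same condition.

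This would matter in a non-inferiority trial. If a recent drop made the arms look alike, readings taken too soon would shrink a real deficit and make it easier to fall below the 2-point margin. The regimen of 3 to 6 drops a day, and visits that may shift by 4 hours either way, mean that scheduling alone does not secure the interval.

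**Working it through.** The main check compares passages. The arithmetic after it shows what the size of the problem would depend on.

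**Tracing the rule through the plan**

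| Step | Where | What it provides |
|---|---|---|
| Rule set | Protocol 6.2.1 | At least 2 hours without IMD before Visits 3 and 4 |
| Hour written down | Protocol 6.4.1.3 | Date and hour of last instillation, in the diary, before each visit |
| Hour looked at | Protocol 6.1.4 and 6.4.1.3 | Diary review and compliance questions, ahead of the slit lamp in a prescribed order |
| Record kept | Protocol 6.5.1 | Diaries are source; the medical record carries compliance from diary and interview |
| Record checked | Protocol 6.5.2 | Monitors review source for compliance with the protocol |
| Breach judged | Protocol 7.1 and 10, SAP 3.2.5 | Blind review before lock, not limited to database values |

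Each step is present. The one thing not stated is where, beyond the diary, the hour is entered at Visits 3 and 4.

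**Does the visible text show that a database field is missing?** It does not.

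- The lists in 6.1.4 are lists of procedures. Those for Visit 2 include randomisation and dispensing, so an item's wording is not a field specification.
- The Visit 2 item is a question to the patient. Nothing shows that it stores an hour either, so the contrast with Visits 3 and 4 is weaker than it looks.
- The footnote is marked at the Visit 1 run-in diary. The IMD diary handed out at Visit 2 carries no such mark.
- eCRF version 4.0, Table 2 and the investigator manual (Protocol 6.4) are not in the supplied text, and the SAP is partly redacted around exposure and compliance.

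**How often could a visit fall within 2 hours of a drop?** Assume a 16-hour waking day (not in the documents), a visit at a random time in it, and patients who ignore the rule.

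- 3 evenly spaced drops, 5.33 to 8 hours apart: 2/8 = 25.0% to 2/5.33 = 37.5%. Of 226 patients, 56.5 to 84.75.
- 6 evenly spaced drops, 2.67 to 3.2 hours apart: 2/3.2 = 62.5% to 2/2.67 = 75.0%. Of 226, about 141 to 170.
- 6 randomly timed drops, visit after the first 2 waking hours: 1 − (14/16)^6 = 55.1%. For a visit within those 2 hours the average is 1 − (16/7)(1 − (14/16)^7)/2 = 30.6%. Overall: (14/16) × 55.1% + (2/16) × 30.6% = 52.1%, about 118 of 226.

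These figures describe a trial in which nobody follows the rule. They are not a breach rate.

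**What could a breach do to the error rate?** Assume a true deficit of exactly 2.0 points, 10% of patients read too soon, and no difference at all between the arms in those patients.

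- Observed difference: 2 × (1 − 0.10) = 1.8.
- Standard error with 113 per arm: SD × √(2/113), which is 0.266 for an SD of 2 and 0.532 for an SD of 4.
- One-sided error at the margin: Φ((2 − 1.8)/SE − 1.96) = 11.3% for an SD of 2 and 5.7% for an SD of 4, against a nominal 2.5%.

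The breach rate, the SD and the erasing effect of one drop are all assumed. The last is the hardest to grant, since Protocol 6.1.3.1 describes staining as a measure of ocular surface damage.

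**The case for a change.** The best case for acting is that the paper trail is uneven. Only 6.4.1.3 asks for the hour. The diary instruction at Visit 2 and the source-data list in 6.5.1 speak of instillations per day, so a site could regard a diary without the hour as complete. Breaches would then reach the blind review only if a site or monitor noticed and reported them. Recording one date and hour at each of two visits is little work: 2 × 226 = 452 entries, or 2 × 250 = 500 for all randomised patients.

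Part of this stands. No visible item at Visits 3 and 4 names the hour, no visible SAP text tests the 2-hour rule, and the reach of the footnote is unclear. But 6.4.1.3 is an explicit protocol requirement, and the shorter lists elsewhere do not cancel it. Reporting of deviations by sites and monitors is an ordinary route into a blind review. The small cost does not establish a need: the form may already hold the hour, and if it does not, the hour can be listed from diaries before the review.

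The 6-hour interval at Visit 2 and the 2-hour interval at Visits 3 and 4 concern different products and different visits. They are not a contradiction, and no view is taken here on either.

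**Conclusion.** No change to the plan follows. This is missing detail about where one item is recorded, and competent data management fills it in the ordinary course. Followed as written, the plan obtains the hour, has it reviewed before the slit lamp, keeps it as source and lets a breach be judged before unblinding. The primary analysis on the full analysis set does not depend on it; only membership of the secondary per-protocol set could.

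The size of any effect is unknown. The documents give no breach rate and no effect of a recent drop on the Oxford score, and the direction is open. The 5.7% to 11.3% range illustrates a set of assumptions and is not evidence of harm.

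The conclusion rests on two readings: that the requirement in 6.4.1.3 is carried out at Visits 3 and 4, and that the blind review may use deviations found in source. A question to the data manager about where the hour is kept, and whether D36 readings taken too soon will be listed for the blind review, would settle what remains.
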